- o For both studies the post-treatment period starts on the day after the treatment period and ends on the day of the patient's last contact date within the study.

• For safety endpoints except for ERG:

- The on-treatment period for the parent study spans the time during which the study treatment is administered from the CS2 Study Day 1 until 7 days after the last dose of medication in the parent study. The on-treatment period for the OLE study is from the CS3 Study Day 1 until 7 days after the last dose of medication in the OLE study.
- For both studies the safety post-treatment period starts on the day after the safety treatment period and ends on the day of the patient's last contact date within the study.
- For both studies the Safety on-study period spans the time drug is first administered until the day of the patient's last contact date within the study.
- The period for the longitudinal safety analysis spans the time from the first dose of ISIS
 420915 in the parent study and ends on the day of the patient's last contact date within the study. The subject's last contact date is defined as follows:
 - (1) for subjects who signed an informed consent form in the OLE study, it is the last contact date within the OLE study;
 - (2) for subjects who did not sign an informed consent form in the OLE study but had been administered ISIS 420915 in the parent study, it is the last contact date within the parent study. The details of longitudinal safety analysis for AEs and safety lab results will be addressed in section 3.3.

For ERG:

The on-treatment period for the parent study spans the time during which the study treatment is administered from the CS2 Study Day 1 until 28 days after the last dose of medication in the parent study. The on-treatment period for the OLE study is from the CS3 Study Day 1 until 28 days after the last dose of medication in the OLE study.

- For both studies the safety post-treatment period starts on the day after the safety treatment period and ends on the day of the patient's last contact date within the study.
- The PK on-study period for the OLE study spans the time ISIS420915 is administered in the OLE study (CS3 Study Day 1) until the day of the patient's last contact date within the OLE study.

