- The Immunogenicity (IM) on-study period for the OLE study spans the time the first dose of ISIS420915 in the parent study and ends on the day of the patient's last contact date within the OLE study. This period is for defining patient IM status (Details in section 3.2.1.1.6).

3.2.1.1.5 Durations of study drug exposure and total dose of ISIS 420915:

Durations of overall drug exposure (days) across both studies will be derived as the difference in
days between the date of the last dose of ISIS 420915 and Day 1 of ISIS 420915 plus one. For
patients who are not enrolled in the OLE study, the last dose of ISIS 420915 is administered in the
parent study; for patients who are enrolled in the OLE study, the last dose of ISIS 420915 is
administered in the OLE study.

The total dose of study drug during the treatment period for either the parent study or the OLE study will be computed for patients receiving ISIS 420915 by summing the dose administered between **Day 1 of ISIS 420915** and the last dose date in the parent study for patients who are not enrolled in the OLE study or the last dose date in the OLE study for patients who are enrolled in the OLE study. Total dose will be summarized in milligrams as part of longitudinal safety analysis.

• Duration of drug exposure in OLE study (days) will be derived as the difference in days between the date of the last dose of ISIS 420915 in OLE study and **CS3 Study Day 1** plus one.

The total dose of study drug during the treatment period for the OLE study will be computed for patients receiving ISIS 420915 in the OLE study by summing the dose assigned between **CS3 Study Day 1** and the EOT date or date of early termination in OLE study. Total dose will be summarized in milligrams.

3.2.1.1.6 *Immunogenicity (IM):*

- For subjects with negative IM status in the parent study, the onset (T_{first}) of anti-ISIS 420915
 antibodies in OLE study will be derived as difference in days between the date when first
 immunogenicity sample becomes confirmed positive (i.e., positive sample IM status) in OLE study
 and Day 1 of ISIS 420915 plus one.
- For subjects with positive IM status in the parent study, the onset (T_{first}) of anti-ISIS 420915 antibodies in the parent study will be used as the onset of the OLE study.

3.2.1.1.7 BMI and mBMI:

• Body mass index (BMI) will be computed using the formula:

BMI = (weight in kilograms) / [height in cm / 100]²

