Safety Endpoints: ERG and ophthalmology examinations	-Listings -On-treatment summary tables (CS3) -Post-treatment summary tables	-On-treatment (CS3 period): CS3 Study Day ls Date of assessment 5 Last dose date+ 28 days -Post-treatment: Date of assessment> last dose date+ 28 days -Visit defined by analysis visit window
Safety Endpoints: abnormal lab, worst ECG, meeting Stopping rule	-Listings -On-study summary tables (CS3)	-Abnormal lab analyses described in Sections 3.3.4.1 to 3.3.4.3 include post-baseline data collected from CS3 Study Day 1 up to the day of the patient's last contact date within the study
Safety Endpoints: AE	-Listings -On-treatment (CS3) summary tables -On-study (CS3) summary tables	-On-treatment: CS3 Study Day ls Date of assessment 5 Last dose date + 7 days -On-study summary tables includes all treatment emergent adverse event (TEAE) in the OLE study, including those with onset dates> last dose date + 7 days
Selected Safety Endpoints: abnormal lab and AEs	- Longitudinal safety summary for overall parent study and OLEstudy	- Longitudinal safety summary for overall parent study and OLE study include data collected from the first dose of ISIS 420915 in the parent study and ends on the day of the patient's last contact date within the study, (1) for subjects who enrolled in the OLE study, it is the last contact date within the OLE study; (2) for subjects who are not enrolled in the OLE study but had been administered ISIS 420915 in the parent study, it is the last contact date within the parent study.
Concomitant medications	-Listings -On-treatment (CS3) summary tables -On-study (CS3) summary table	-On-treatment: CS3 Study Day ls Date of assessment s Last dose date + 7 days -On-study summary tables includes all concomitant medication in the OLE study, including those with onset dates > last dose date+ 7 days
Immunogenicity	-Listings -On-study (CS2 and CS3)	-On-study summary/analysis tables include data collected from the CS2 Study Day 1 up to the day of the

Endpoint type	Output type	Comment/definition
	summary/ analysis tables	patient's last contact date within the study (showing both CS2 visits and CS3 visits) -Visit defined by analysis visit window.
PK	-Listings -On-study (CS3) summary/ analysis tables	-Summary/analysis tablesinclude data collected from CS3 Study Day 1 up to the day of the patient's last contact date within the study -PK concentration will be summarized based onnominal scheduled visits (showing CS3 visits)

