3.2.2 Patient Populations Analyzed

The following analysis populations are defined for this present OLE study:

- Screened patients will be defined as patients who signed an informed consent form.
- Enrolled patients will be defined as patients who signed an informed consent form and were not screen failures.
- The FAS will include all enrolled patients who received at least 1 injection of ISIS420915 in the
 OLE study and who have at least one post-baseline efficacy assessment for the mNIS+7 score or
 Norfolk QOL-DN questionnaire total score collected after CS3 Study Day 1 in this OLE study. This
 will be the primary population for analysis of efficacy and PD outcomes.
- The Safety Set (SS) will include all enrolled patients who received at least 1 injection of ISIS
 420915 in the OLE study. This population will beused for analyses of all safety measures
 collected in this OLE study. Results will be summarized under the treatment which the patients
 received in the parent study.
- The Longitudinal Safety Set (LSS): will include all patients who received at least 1 injection of ISIS 420915 in the parent study. This population will beused for the longitudinal safety analysis for either the parent study or this OLE study. Results will besummarized under the treatment which the patients received in the parent study. Note that this population will include patients who receive ISIS 420915 in the parent study but did not enter this OLE. It does not include patients who took placebo in CS2.
- The PPS will include the subset of the Full Analysis Set that have received at least 70% of the prescribed doses of ISIS 420915 in this OLE study and that have no significant protocol deviations in the OLE study that would be expected to affect efficacy assessments. Prescribed doses of ISIS420915 mentioned above is defined as the total assigned dose in mg from the Week 1 to the last dose within this study up to week 156 (first three years), i.e. 300mg*156 doses= 46800mg. Patients in FAS of this OLE study but excluded from PPS in the parent study will be excluded from the PPS in this OLE study as well. This will be a secondary population for

efficacy and PD analyses. The detailed criteria and definitions for major protocol violations will be specified. Results will be summarized under the treatment which the patients received in the parent study.

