3.3.2.7 Longitudinal Safety Analysis of TEAEs

For this summary TEAEs are defined as those events which first occurred or worsened on or after first dose of ISIS in the parent study.

Adverse events summaries including data from the combined study periods of the parent and OLE studies will be provided for subjects in the LSS analysis population. These summaries will include all TEAEs which started on or after the first dose of ISIS 420915 in the parent study and before the day of the patient's last contact date. For subjects who enrolled in the OLE study, the last contact date would be the one obtained from the OLE study. For subjects who are not enrolled in the OLE study the last contact date would be the one obtained from the parent study. Note that AEs which started during the gap period between the completion of the parent study and the first dose of the OLE study and are not considered TEAEs in the OLE study will still be included in these summaries. In other words, it is possible that there will be events which are not considered parent study TEAEs or OLE study TEAEs, but will be counted towards this analysis.

These TEAEs will be summarized for subgroups defined by the following variables: Age at parent study screening (<65 years and >=65 years), Sex (Female and Male), Race, Region (North America, Europe and South America /Australasia), and CM-ECHO Set (Included and Not Included). Results will not be provided for a variable if the overwhelming majority of patients are within one level of the subgroup.

Summaries of drug related TEAEs, TEAEs by maximum severity, adverse events leading to early withdrawal from Study Drug, TEAEs duration of exposure to Study Drug at the start of event (< 6 months, \geq 6 months to < 12 months, \geq 12 months to < 24 months, \geq 24 months to < 36 months, \geq 36 months to < 48 months, \geq 48 months to < 60 months, and \geq 60 months)and Number of doses at the start of event (26, \geq 26 to < 52, \geq 52 to < 65, \geq 65 to < 104, \geq 104 to < 156, \geq 156 to < 208, \geq 208 to < 260, \geq 260) will also be provided. Duration of exposure and the number of doses is calculated from **Day 1 of ISIS 420915** to the start date of event.

TEAEs in the following categories will also be summarized in tables and listed separately:

- Adverse events of special interest (defined in section 3.3.2.1)
- Other adverse events of interest (defined in section 3.3.2.2)

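### The longitudinal safety end date follows OLE consent in one SAP section and OLE enrolment in three others, and neither rule suits patients never dosed in the OLE

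*Combined protocol and SAP*

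**What the plan says.** The longitudinal safety analysis covers the Longitudinal Safety Set (LSS): everyone who received ISIS 420915 in the parent study, expressly including those who did not go on to the OLE (SAP 3.2.2). The SAP states in four places which study supplies the last contact date that closes the period.

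- **SAP 3.2.1.1.4** decides by consent. The OLE date applies "for subjects who signed an informed consent form in the OLE study, it is the last contact date within the OLE study". The parent-study date applies "for subjects who did not sign an informed consent form in the OLE study but had been administered ISIS 420915 in the parent study".
- **SAP 3.2.1.4** decides by enrolment. The OLE date applies "for subjects who enrolled in the OLE study, it is the last contact date within the OLE study". The parent-study date applies "for subjects who are not enrolled in the OLE study but had been administered ISIS 420915 in the parent study".
- **SAP 3.3.2.7** (adverse events) also uses enrolment: "For subjects who are not enrolled in the OLE study the last contact date would be the one obtained from the parent study".
- **SAP 3.3.4.4** (laboratory data) repeats the enrolment rule.

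SAP 3.2.2 separates the two terms. Screened means consent was signed, whereas "Enrolled patients will be defined as patients who signed an informed consent form and were not screen failures". A first OLE dose is not part of that definition. Protocol 4.1, by contrast, treats a patient as enrolled from the moment of consent.

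For overall exposure and total dose, SAP 3.2.1.1.5 also branches on enrolment: "for patients who are enrolled in the OLE study, the last dose of ISIS 420915 is" the one given in the OLE.

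**The concern.** Consent, enrolment and first OLE dose are three different events, and the SAP uses the first two interchangeably to decide which study closes a patient's safety record. They separate in patients treated with ISIS 420915 in the parent study who signed the OLE consent but were never dosed there. Such patients stay in the LSS, and SAP 3.2.1.3 confirms that the parent study has its own post-treatment evaluation period. If the period is closed at an OLE screening contact, any later parent-study follow-up falls outside the longitudinal tables.

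Safety is the primary objective, and failure to enter the OLE is partly related to safety. Protocol 5.1 requires no significant tolerability problems, and the only exclusion criterion in Protocol 5.2 is a new or worsening condition. Protocol 6.1.3 requires platelet and creatinine testing for at least 6 weeks after the last OLE dose, so the plan itself treats the weeks after stopping as a time to watch.

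**Working it through.** The plan gives no figure to reproduce. The check sets the rules side by side, then states when data are lost.

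**Step 1. Which study supplies the end date, for LSS patients never dosed in the OLE** (enrolled as in SAP 3.2.2)

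| Patient | SAP 3.2.1.1.4 (consent) | SAP 3.2.1.4, 3.3.2.7, 3.3.4.4 (enrolment) | Result |
|---|---|---|---|
| (a) No OLE consent | Parent study | Parent study | Consistent, nothing lost |
| (b) Consented, screen failure | OLE | Parent study | Conflict |
| (c) Consented, not a screen failure, undosed | OLE | OLE | Consistent, but can truncate |

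If a programmer used the Protocol 4.1 meaning of enrolled, (b) would get the OLE date in every section.

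**Step 2. When follow-up is lost.** For (b) under 3.2.1.1.4, and for (c):

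days lost = max(0, last parent-study contact − last OLE contact).

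Parent-study data up to the last OLE contact stay in. If the OLE contact is the later date, nothing is lost.

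**Step 3. Illustration per patient.** Two inputs are assumptions. Parent-study follow-up is taken as 13 weeks (91 days), borrowed from the OLE because the documents do not give the parent study's own. The last OLE contact is taken as 0 to 28 days after the last parent-study dose, in line with the 4-week interval in Protocol 6.1.1.

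- Days lost: 91 − 28 = 63, to 91 − 0 = 91 (9 to 13 weeks).
- Set against a 6-week (42-day) monitoring span such as Protocol 6.1.3 uses after the last OLE dose: 42 − 28 = 14, to 42 − 0 = 42 days fall outside the period.

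**Step 4. Illustration for the analysis set.** About 90 patients were planned for the active arm of the parent study (SAP 1.1). The share who consented but were not dosed in the OLE is not given; 2% to 10% is assumed.

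- Patients: 90 × 0.02 = 1.8, to 90 × 0.10 = 9.
- Person-time: 1.8 × 9 = 16 person-weeks, to 9 × 13 = 117 person-weeks (0.3 to 2.2 person-years).
- Effect of one missed first event on a longitudinal percentage: 1/90 = 1.1 points.

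These ranges hold only if such patients exist and every one of them loses follow-up. The floor is zero.

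**Step 5. Exposure.** SAP 3.2.1.1.5 computes overall exposure as last ISIS 420915 dose date − Day 1 of ISIS 420915 + 1, and sums dose over the same span. For patient (c) the last dose is to come from the OLE, where no dose was given. Both quantities are then undefined, although the parent-study dosing record exists.

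**The case against.** The case against has several sound parts.

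- **Section 3.3 may be read as controlling.** SAP 3.2.1.1.4 refers to section 3.3 for the details, and 3.3.2.7 and 3.3.4.4 use enrolment. With the SAP's own definition, screen failures then keep their parent-study date. That is a fair reading, and a reader who infers that every consented but undosed patient loses follow-up goes too far. It does not remove the contradictory text, and it does nothing for the enrolled but undosed patient.
- **SAP 9.2.2.2 has no such branch.** For the combined parent-study and OLE summaries it ends the on-study period at the patient's last contact. But it does not say which study supplies that contact, and it declares itself not in conflict with 3.2.1.1.4. SAP 9.1 does not withdraw the analyses in 3.3.2.7 or 3.3.4.4. Section 9.2.2 also refers to a separate integrated safety SAP that is not among these documents. This eases the problem without curing it.
- **A cut at or before the last parent-study dose.** A reader might infer this from the nominal Day −28 to −1 screening window and the ideal one-week gap between studies. The documents do not support it well. Protocol 6.1.1 and footnote 1 of Appendix A place screening assessments between the last parent-study dose and OLE Day 1, and inclusion criterion 1 requires parent-study dosing and end-of-treatment efficacy assessments to be complete.
- **A threat to the main safety results.** This does not follow either. OLE safety tables use the Safety Set, which requires an OLE dose. The parent study keeps its own on-study safety period to last contact, so these events remain within that study's own safety period.
- **Selection for safety problems is only partial.** Eligibility also turns on compliance, vitamin A, contraception and consent.

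**Conclusion.** The inconsistency is real and visible in the SAP text. A consented screen failure from the former active arm has two conflicting end dates. An enrolled but undosed patient is closed at the OLE contact under every statement of the rule and has no defined last dose. In both cases a stated rule can remove parent-study follow-up from the longitudinal safety tables, provided the last OLE contact precedes the last parent-study contact.

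The documents do not show that any follow-up was lost. The number of affected patients may be zero, they do not establish that such patients entered parent-study follow-up, and the length of that follow-up is not given. The person-time figures above therefore illustrate a possible scale and do not estimate a loss. The effect is confined to the longitudinal tables. It should be corrected because the text does not tell a programmer which date to use and the correction is nearly free.

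**What to change.** In SAP 3.2.1.1.4, 3.2.1.4, 3.3.2.7 and 3.3.4.4, use one definition: the longitudinal period ends at the later of the last parent-study contact and the last OLE contact. Remove the consent and enrolment conditions. In SAP 3.2.1.1.5, define the last dose for overall exposure and total dose as the latest ISIS 420915 dose actually given in either study. SAP 9.2.2.2 can then refer to the same end date.

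The cost is SAP wording and one derivation, the maximum of two dates, with the matching rule for last dose. No new data are needed, and results should not change for patients dosed in the OLE or for those who never consented to it.

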3.6.2 Immunogenicity (IM) Analyses

Samples collected during treatment and post-treatment period, including early termination and unscheduled samples for IM assessment as specified in the study protocol will be analyzed for ADA. However, plasma samples collected at other time points (or for PK purposes) may also be potentially evaluated if deemed of further interest and warranted by the pharmacokinetic scientist. Samples that are confirmed IM positive are subjected for titering, which may include but not limited to the samples collected on Days 85, 176, 358, 540, 722, or 1086 during treatment period.

An evaluable sample will be designated 'IM positive' based on both positive screening and confirmation assay results (i.e., confirmed positive result); otherwise, the sample will be deemed 'IM negative'. Sample IM results (screen positive/negative, confirmed positive/negative or unevaluable, and when applicable, titer of anti-ISIS 420915 antibodies) during and after treatment with study drug (ISIS 420915) (sample IM status) will be listed by the subject's prior treatment in the parent study, dose, and study day.

Patient IM status: Study patients will be given 'IM positive' status if they have at least one confirmed positive sample result at any time during the treatment or post-treatment evaluation periods. Study patients will be given 'IM negative' status if all evaluated IM sample results during the treatment and post-treatment evaluation periods are IM negative and they have at least one evaluable IM result collected post study drug treatment. Otherwise, a study patient will be given 'unknown' IM status. Subject IM results will be listed by treatment group of the parent study and dose for all evaluable patients, which will include but may not be limited to: patient IM status (positive, negative or unknown), the day associated with the first positive IM status emerged since receiving ISIS 420915 treatment (T_{first}, i.e., onset of ADA development as described below), the last positive IM status observed (T_{last}), the last evaluable IM sample collected (T_{last sampling}), peak titer, and time to reach peak titer.

Onset of immunogenicity: The onset (T_{first}) of anti-ISIS 420915 antibodies for OLE study will be derived as the difference between the date when first immunogenicity sample becomes confirmed positive (i.e., positive sample IM status) and Day 1 of ISIS 420915 plus one.

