The sample IM incidence (number) and incidence rate (percent) at each evaluated study time point, and for the overall treatment and post-treatment evaluation period, as well as subject IM incidence and incidence rate, will be determined and appropriately summarized by treatment group of the parent study, as the total number of and percentage of evaluated subjects with IM negative, positive, and unknown status. Subjects with positive IM status may further be classified as transient or persistent status if applicable, with incidence and incidence rate being transient or persistent appropriately summarized. Furthermore, onset, titer over time, peak titer of the ADA response, and time to reach peak titer, if applicable, will be also appropriately summarized (using descriptive statistics) as median, quartiles (25% and 75%), and range and presented graphically, if deemed appropriate, by treatment group of the parent study (e.g., summarized at each evaluated study time point and overall; summarized by observed peak titer values from the individual IM positive patients; etc.).

- Onset in days = The date of first sample has "positive" sample IM status Day 1 of ISIS 420915
 +1;
- Time to reach peak titer in days = The date of peak titer observed- Day 1 of ISIS 420915 +1;

In addition to PK assessments (Section 3.6.1), selected efficacy (Sections 3.4 to 3.5) and safety (Section 3.3) assessments will also be further stratified by patient IM status (i.e., patient IM status being positive, negative, or unknown) and presented in tables and/or graphically, as deemed appropriate or warranted by the designated study pharmacokineticist, medical monitor, and/or biostatistician. Efficacy measures to be stratified by patient IM status will include, but may not be limited to, TTR level, mNIS+7, and Norfolk QOL-DN score. Safety measures to be stratified by patient IM status will include, but may not be limited to, AEs, and lab tests for hematology and kidney functions.

Other stratifications (e.g., based on antibody titer, onset of ADA, etc.) of selected PK, efficacy and safety assessments may also be performed if deemed warranted at the discretion of the pharmacokineticist, medical monitor, and/or biostatistician.

4. Sample Size

No sample size calculations were performed as this is an extension study to the double-blind, placebo-controlled ISIS 420915-CS2 study. Approximately 135 patients were planned to be eligible to enroll into this present OLE study.

5. Interim Analyses

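### Ever-positive antibody incidence is tabulated by parent treatment group over unequal time on drug, so at equal seroconversion rates the former-active percentage is expected to be higher, or at best equal

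*Combined protocol and SAP*

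**What the plan says.** SAP 3.2.1.1.4: "The Immunogenicity (IM) on-study period for the OLE study spans the time the first dose of ISIS420915 in the parent study". The window ends at the patient's last OLE contact, and its stated purpose is to define patient IM status.

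The immunogenicity row of the table in SAP 3.2.1.4 gives a different start: "On-study summary/analysis tables include data collected from the CS2 Study Day 1 up to the day of the" last contact, with CS2 and CS3 visits both shown. SAP 3.2.1.1.1 defines CS2 Study Day 1 as the first day of study drug, active or placebo.

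SAP 3.6.2 makes status ever-positive: "Study patients will be given 'IM positive' status if they have at least one confirmed positive sample result at any time" during or after treatment. Subject incidence is then "summarized by treatment group of the parent study, as the total number of and percentage of evaluated subjects with IM negative, positive, and unknown status". The term incidence rate means a percentage here, as in "The sample IM incidence (number) and incidence rate (percent) at each evaluated study time point". No person-time rate, time-to-event estimate or equal-exposure window is planned.

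For patients already positive in CS2, SAP 3.2.1.1.6 carries the result forward: the onset of "antibodies in the parent study will be used as the onset of the OLE study".

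Onset and time to peak titer are counted from Day 1 of ISIS 420915 (SAP 3.2.1.1.6 and 3.6.2). That day falls in CS2 for former-active patients and in the OLE for former-placebo patients (SAP 3.2.1.1.1).

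**The concern.** An ever-positive classification can only rise with time on drug and number of samples. The by-group table sets patients whose window covers CS2 treatment plus the OLE beside patients who are on drug only in the OLE. Part of any difference between the columns is then exposure time.

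The plan avoids this elsewhere. OLE adverse events, abnormal laboratory results and PK are summarised from CS3 Study Day 1 for both groups (SAP 3.2.1.4). The longitudinal safety analysis, which does add CS2 time on drug, leaves out CS2 placebo patients (SAP 3.2.2), so it never shows unequal windows side by side.

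There is also a wording defect that needs no assumption. Former-placebo patients have no ISIS 420915 dose in the parent study, so SAP 3.2.1.1.4 gives them no start date. SAP 3.2.1.4 starts them in placebo time. The two cannot both define the period.

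Immunogenicity is among the safety laboratory tests (SAP 3.3.4), and safety is the primary objective. A reader might take a higher former-active percentage as a group difference in immunogenicity, for example an effect of the three Week 1 doses in CS2 against one in the OLE (SAP 1.1).

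**Working it through.** **Time on drug.** Protocol 2.4: 65 + 260 = 325 weeks for former-active patients, the stated figure. SAP 1.1: 65 + 156 = 221 weeks, also as stated. Former-placebo patients have 260 or 156 weeks. The excess is 65 weeks either way: 65/221 = 29% of the former-active time on drug, or 65/325 = 20%.

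**Assumptions.** The documents give no seroconversion rate or onset pattern. Let p65 be the cumulative incidence after 65 weeks on drug, varied from 10% to 40%. Both groups have the same rate and equal OLE follow-up, and the spacing of samples is ignored.

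**Constant hazard.** h = −ln(1 − p65)/65 and F(t) = 1 − exp(−h·t). At OLE week w, former-placebo patients show F(w) and former-active patients F(w + 65). For p65 = 20%, h = 0.2231/65 = 0.00343. At w = 156, F(156) = 41.5% and F(221) = 53.2%, a gap of 11.7 points.

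Each cell gives former-placebo % vs former-active %, with the gap in points from unrounded values:

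| p65 | OLE week 26 | OLE week 156 | OLE week 260 |
|---|---|---|---|
| 10% | 4.1 vs 13.7 (9.6) | 22.3 vs 30.1 (7.8) | 34.4 vs 41.0 (6.6) |
| 20% | 8.5 vs 26.8 (18.3) | 41.5 vs 53.2 (11.7) | 59.0 vs 67.2 (8.2) |
| 30% | 13.3 vs 39.3 (26.0) | 57.5 vs 70.3 (12.7) | 76.0 vs 83.2 (7.2) |
| 40% | 18.5 vs 51.1 (32.6) | 70.7 vs 82.4 (11.7) | 87.0 vs 92.2 (5.2) |

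At week 156 the constant-hazard gap has a ceiling. It is largest when p65 = 65/221 = 29.4%, where it equals (156/221)^(156/65) × 65/221 = 0.4335 × 0.2941 = 12.7 points.

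**Front-loaded conversion (Weibull, shape 0.5).** With p65 = 30% the gaps are 14.2 points at week 26, 5.7 at week 156 and 4.0 at week 260. Fixing instead 30% at 156 weeks in former-placebo patients gives 1 − exp(ln(0.7) × (221/156)^0.5) = 34.6% in former-active patients, a gap of 4.6 points.

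**Early conversion with a plateau.** F(t) = 35% × (1 − 0.5^(t/m)), with half of eventual conversions by m = 13 to 52 weeks. The gap is 8.5 to 15.1 points at week 26, 0.0 to 2.5 at week 156, and at most 0.6 at week 260.

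**After the fix.** Counted over the same number of weeks from Day 1 of ISIS 420915, equal rates give a gap of 0 by construction. Under the constant hazard, first positives per patient-year on drug also agree: for p65 = 20%, 0.00343 × 52 × 100 = 17.9 per 100 patient-years in both groups.

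**The case against.** The strongest reply is that nothing is tested and much is already aligned.

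- SAP 1.3 states that there are no formal hypotheses, and no objective compares antibody incidence between parent arms. This stands: it is not a type I error problem.
- Onset and time to peak share a common origin, so it would be wrong to say these measures start at different points. What remains unequal is how long patients are observed.
- For combined CS2 and CS3 summaries, SAP 9.2.2.2 starts the on-study period at ISIS 420915 Study Day 1, and SAP 9.2.2.4 lists subject IM incidence on that basis. SAP 9.2.2 defers detail to a separate ISS SAP that is not among the documents, so how those tables handle length of exposure is unknown. SAP 9.2.2.2 limits its definition to combined data and leaves the OLE tables as they are.
- Sample incidence by time point is planned, with CS2 and CS3 visits shown. A reader could set former-active CS2 visits beside former-placebo OLE visits. That helps, but it gives point prevalence rather than cumulative incidence. At the same OLE visit the 65-week difference remains.
- Carrying CS2 positives forward is reasonable, since restarting status in the OLE would misclassify them. The fix keeps that rule.
- The groups are small. With the planned maximum of 45 and 90 patients (SAP 1.1), 30% against 40% has a 95% half-width of 1.96 × √(0.3×0.7/45 + 0.4×0.6/90) = 17 points. Chance can hide or exaggerate the artefact but does not remove it.

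A reader might infer more: that every former-active patient has 65 extra weeks, that this column will certainly show more positives and higher peak titers, or that a group effect could never be separated. The documents do not support this. Protocol 5.1 admits some patients who did not complete CS2 treatment. It also requires no significant tolerability issues in CS2, which selects former-active patients on drug tolerance and could act the other way. Nothing in the documents allows an effect on peak titer to be computed.

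**Conclusion.** The point holds as a risk of misreading in a descriptive safety table. With equal seroconversion rates and equal OLE follow-up, the former-active ever-positive percentage is expected to be higher than the former-placebo percentage, and cannot be lower.

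The size rests wholly on assumed onset patterns. At OLE week 156 it is roughly 5 to 13 points if conversion continues, and 0 to 2.5 points if conversion is early and plateaus. At OLE week 26 the same scenarios give 8.5 to 32.6 points. That matters for the interim analyses that tabulate patient IM status, at parent-study EOT and for the Day-90 update (SAP 5.1 and 5.2), to the extent that OLE follow-up was short.

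The mismatch between SAP 3.2.1.1.4 and 3.2.1.4 on the start date for former-placebo patients stands without any assumption. The change is worth making because it uses data already held, but no conclusion of a formal test depends on it.

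**What to change.** 1. In SAP 3.2.1.1.4 and 3.2.1.4, start the IM period at Day 1 of ISIS 420915 for every patient: CS2 Study Day 1 for former-active and CS3 Study Day 1 for former-placebo patients. SAP 9.2.2.2 already does this for combined data, and it removes the conflict between the two sections.
2. In SAP 3.6.2, keep the ever-positive table by parent treatment group and footnote the unequal time on drug.
3. In SAP 3.6.2, add cumulative incidence of first confirmed positivity by group and weeks since Day 1 of ISIS 420915, at common times (for example 26, 52, 104 and 156 weeks), censoring at the last evaluable sample. Results after 156 weeks need not be dropped from the by-group tables.

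The cost is SAP wording and one or two extra tables. The dates needed are already used for onset and for the last evaluable sample, so no new data are required. One limitation remains: Protocol Appendix A schedules immunogenicity samples once a year in Years 4 and 5, so late conversions will be timed only coarsely.
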